5.2.4. Methotrexate in Arm B

5.2.4.1. Dose modifications

The following dose levels will be used in modifying the dose of methotrexate:

Table 13: Dose reduction of methotrexate in Arm B

Dose level	Methotrexate
0 (starting dose)	40 mg/m ²
- 1	30 mg/m ²
- 2	20 mg/m ²

Patients requiring dose reductions to less than 20 mg/m² must be discontinued with the exception of responding patients after consultation and approval by the sponsor.

5.2.4.2. Treatment modifications for haematological toxicity

Complete blood cell counts will be performed before each administration of methotrexate.

Cycle delay

Dosing is considered delayed if Day 1 treatment has been performed:

- either $\geq 21 + 4$ days since last Day 1 study drug administration (i.e., Day 26 or more).
- or $\geq 14 + 4$ days since last Day 8 study drug administration
- or $\geq 7 + 4$ days since last Day 15 study drug administration

Neutrophil count should be $\geq 1.5 \times 10^9/L$ (grade 1) and platelet count $\geq 100 \times 10^9/L$ before each new cycle (day 1 administration) as shown below.

Table 14: Arm B - Dose delay of methotrexate on day 1 for haematological toxicity

Haematological toxicity before day 1 administration			Day 1 administration of study treatment
Absolute neutrophils		Platelets	
$ANC \geq 1.5 \times 10^9/L$	and	$\geq 100 \times 10^9/L$	No dose modification. Treat on time
$ANC < 1.5 \times 10^9/L$	and / or	$< 100 \times 10^9/L$	Delay cycle and reassess one week later

If recovery has not occurred after a 2-week delay, the treatment will be discontinued unless approved by the sponsor.

Dose delay / cancellation of methotrexate at days 8 and 15

This protocol does not allow other cases of dosing delay of methotrexate. Any delay of a methotrexate dosing done outside of this above rule (also shown in Table 10) will be recorded as a delay and as a protocol deviation, (≥ 4 days with respect to the planned day).

The days 8 and 15 administrations should be cancelled if neutrophils count are $< 1.5 \times 10^9/L$ and/or platelet count $< 100 \times 10^9/L$ as shown below.

Table 15: Dose cancellation of methotrexate within a cycle in Arm B

Haematological toxicity before administration			Arm B	
Absolute Neutrophils		Platelets	Day 8	Day 15
$ANC \geq 1.5 \times 10^9/L$	and	$\geq 100 \times 10^9/L$	Treat on time	Treat on time
$ANC < 1.5 \times 10^9/L$	and / or	$< 100 \times 10^9/L$	Dose cancellation	Dose cancellation

Dose modifications

Table 16 details severe haematological toxicity which must lead to dose reduction.

Table 16: Dose modifications of methotrexate in Arm B for haematological toxicity

Haematological toxicity after the previous administration	Dose adjustment for next administration
Grade 3 thrombocytopenia (platelets $\geq 25 \times 10^9/L$ and $< 50 \times 10^9/L$) with significant bleeding or requiring transfusion	First appearance : reduce one dose level Second appearance : reduce two dose levels Third appearance : stop treatment
Grade 4 thrombocytopenia (platelets $< 25 \times 10^9/L$)	
Grade 4 neutropenia (ANC $< 0.5 \times 10^9/L$) lasting ≥ 5 days	
Neutropenic infection (grade ≥ 3 neutropenia concomitant with grade ≥ 3 infection)	
Febrile neutropenia of any grade	

5.2.4.3. *Treatment modifications for non haematological toxicity*

The non haematological adverse events which may require treatment modifications include :

- stomatitis
- increased transaminases
- and less often, nausea, vomiting, diarrhoea and skin rash.

Cycle delay

Rules defining the cycle delay are the same as outlined in section 5.2.4.2.

Day 1 administration must be delayed in case of grade > 1 stomatitis or grade > 1 increase of transaminases ($> 2.5 \times ULN$). Methotrexate must not be readministered before total recovery.

If recovery requires more than 2 weeks, methotrexate should be permanently discontinued.

Dose cancellation (days 8 and 15)

Administration on days 8 and 15 in arm B must be cancelled in case of grade > 1 stomatitis or grade > 1 increase of transaminases (> 2.5 x ULN).

This protocol does not allow other cases of dosing delay of methotrexate. Any delay of a methotrexate dosing done outside of this above rule (also shown in Table 10) will be recorded as a delay and as a protocol deviation, (≥ 4 days with respect to the planned day).

Dose modifications

The table below outlines dose reduction for non-haematological toxicity.

Table 17: Dose modifications of methotrexate in Arm B for non-haematological toxicities

Non haematological toxicity after the previous administration	Dose adjustment for next administration
Stomatitis Grade 1 Grade 2 Grade ≥ 3	Maintain the same dose Decrease one dose level Decrease two dose levels
Transaminases > 2.5 x ULN and ≤ 5.0 x ULN > 5.0 x ULN and ≤ 20 x ULN	Decrease one dose level Decrease two dose levels
Decreased creatinine clearance (Cockcroft-Gault) ≤ 60 mL/min and ≥ 20 mL/min < 20 mL/min	Decrease one dose level Discontinue treatment
Other grade $\geq 3^*$ toxicities	To be adjusted as medically indicated

* except grade 3 fatigue

5.2.5. Discontinuation of vinflunine or methotrexate in Arm A due to toxicity

Patients in arm A who require discontinuation of methotrexate may remain on vinflunine alone for the remainder of the study. Likewise, patients who require discontinuation of vinflunine may remain on methotrexate alone for the remainder of the study.

The patients who require discontinuation of methotrexate must continue with vinflunine at the current dose level for at least one more cycle. For patients who require discontinuation of vinflunine, methotrexate dosing must be increased to 40 mg/m² for at least one more cycle. Thereafter,

- if toxicity subsequently occurs, that requires treatment modifications of methotrexate, rules described in Arm B should apply (Table 16, Table 17).

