9. Adequate haematological function: absolute neutrophil count (ANC) \geq 1.5 x 10⁹/L, platelets \geq 100 x 10⁹/L, haemoglobin \geq 10g/dL.

10. Adequate hepatic function: transaminases \leq 2.5 x Upper Limit of Normal (ULN), total bilirubin \leq 1.5 x ULN, alkaline phosphatase \leq 5 x ULN

11. Adequate renal function: calculated (Cockcroft-Gault) creatinine clearance > 60 ml/min

12. Women of childbearing potential must be using a medically accepted method of contraception (barrier methods, oral contraceptives, intrauterine devices) to avoid pregnancy during the 2 months preceding the start of study treatment, throughout the study period and for up to 3 months after the last dose of study treatment in such a manner that the risk of pregnancy is minimised. Women of childbearing potential must have a negative serum or urine pregnancy test within 72 hours prior to first treatment administration

13. Fertile men must be using adequate contraceptive measures throughout the study period and for up to 3 months after the last dose of study treatment if their partner are women of childbearing potential

14. The patient must have access to social insurance if applicable in the local regulations

15. Absence of any psychological, familial, sociological or geographical condition potentially hampering compliance with the study protocol and follow-up schedule, those conditions should be assessed with the patient before registration in the trial.

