5.2.1. General considerations

After any dose reduction, this dose is then maintained with no re-escalation of doses in subsequent cycles.

Re-treatment may be delayed by one week up to 2 weeks pending recovery. Any patient who requires a delay of more than 2 weeks, for whatever reason, will be taken off study.

In case of toxicity, all dosing adjustment or delay should be applied to both drugs of arm A unless there is another specific recommendation.

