Therefore, specific recommendations for treatment modifications for each of these adverse events are provided in this section.

Rare cases of Posterior Reversible Encephalopathy Syndrome (PRES) have been observed after administration of vinflunine. The typical clinical symptoms and signs are, with various degrees: neurological (headache, confusion, seizure, visual disorders), systemic (hypertension), and gastrointestinal (nausea, vomiting). Radiological signs are white matter abnormalities in the posterior regions of the brain. Clinical and radiological features usually resolved rapidly without sequelae after treatment discontinuation.

Vinflunine must be discontinued in patients who develop neurological signs of PRES.

Cycle delay

Rules defining the cycle delay are the same as outlined in section 5.2.2.2.

All non-haematological toxicity, except alopecia and fatigue should be resolved to grade ≤ 1 prior to starting a new cycle of treatment.

If grade ≥ 3 toxicity persists for more than 2 weeks, the study drug should be permanently discontinued.

Dose modifications

The table below outlines dose modifications for non-haematological toxicity.

Table 7: Dose modifications for non-haematological toxicity

Non haematological toxicity during the previous cycle	Dose adjustment for next cycle
Constipation	
Grade 2	Maintain treatment at the same dose Adjust laxative therapy*
Grade 3	Decrease one dose level Adjust laxative therapy*
Grade 4	Discontinue treatment
Stomatitis	
Grade 2	Maintain treatment at the same dose
Grade ≥ 3	Decrease one dose level
Peripheral neuropathy	
Grade 2	Decrease one dose level
Grade ≥ 3	Discontinue treatment
Other grade $\geq 3^{**}$ toxicities	To be adjusted as medically indicated after discussion between investigator and sponsor
Hyperbilirubinemia	
Grade 2 ($> 1.5 \times \text{ULN}^{***}$ and $\leq 3.0 \times \text{ULN}$)	Decrease dose to 250 mg/m^2
Grade 3 ($> 3.0 \times \text{ULN}$)	Delay treatment until recovery to grade 2 and resume at 250 mg/m^2
Decreased creatinine clearance (Cockcroft-Gault)	
$< 40 \text{ ml/min}$ and $\geq 20 \text{ ml/min}$	Decrease dose to 250 mg/m^2
$< 20 \text{ ml/min}$	Discontinue treatment

* Give a stimulant and a stool softener

** Except grade 3 fatigue

*** Upper limit of normal

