5.2.3.2. Treatment modifications for haematological toxicity

Complete blood cell counts will be performed before each administration of methotrexate.

Cycle delay

Cycle is considered delayed if Day 1 treatment has been performed:

- either $\geq 21 + 4$ days since last Day 1 study drug administration (i.e., Day 26 or more).
- or $\geq 14 + 4$ days since last Day 8 study drug administration

Neutrophil count should be $\geq 1.5 \times 10^9/L$ (grade 1) and platelet count $\geq 100 \times 10^9/L$ before each new cycle (day 1 administration) as shown below.

Table 9: Arm A- Dose delay of methothrexate on day 1 for haematological toxicity

Haematological toxicity before day 1 administration			Day 1 administration of study treatment
Absolute neutrophils		Platelets	
ANC $\geq 1.5 \times 10^9/L$	and	$\geq 100 \times 10^9/L$	No dose modification. Treat on time
ANC $< 1.5 \times 10^9/L$	and / or	$< 100 \times 10^9/L$	Delay cycle and reassess one week later

Dose delay / cancellation of methotrexate at day 8

If neutrophils count are $< 1.5 \times 10^9/L$ and/or platelets count $< 100 \times 10^9/L$, the day 8 administration should be delayed 1 week, to day 15. If no recovery after reassessment one week later, the dosing should be cancelled (Table 10).

This protocol does not allow other cases of dosing delay of methotrexate. Any delay of a methotrexate dosing done outside of this above rule (also shown in Table 10) will be recorded as a delay and as a protocol deviation, (≥ 4 days with respect to the planned day).

Table 10: Dose delay or cancellation of methotrexate at Day 8 in Arm A

Haematological toxicity before administration			
Absolute Neutrophils		Platelets	Day 8
$ANC \geq 1.5 \times 10^9/L$	and	$\geq 100 \times 10^9/L$	Treat on time
$ANC < 1.5 \times 10^9/L$	and / or	$< 100 \times 10^9/L$	Delay 1 week and reassess. If no recovery, dose must be cancelled

Dose modifications

Table 11 details severe haematological toxicity which must lead to dose reduction.

Table 11: Dose modifications of methotrexate for haematological toxicity in Arm A

Haematological toxicity after the previous administration	Dose adjustment for next administration
Grade 3 thrombocytopenia (platelets $\geq 25 \times 10^9/L$ and $< 50 \times 10^9/L$) with significant bleeding or requiring transfusion	First appearance : reduce one dose level
Grade 4 thrombocytopenia (platelets $< 25 \times 10^9/L$)	
Grade 4 neutropenia (ANC $< 0.5 \times 10^9/L$) lasting ≥ 5 days	

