Neutropenic infection (grade ≥ 3 neutropenia concomitant with grade ≥ 3 infection)	Second appearance: stop MTX
Febrile neutropenia of any grade	

5.2.3.3. *Treatment modifications for non-haematological toxicity*

The non haematological adverse events which may require treatment modifications include:

- stomatitis
- increased transaminases
- and less often, nausea, vomiting, diarrhoea and skin rash.

Cycle delay

Rules defining the cycle delay are the same as outlined in section 5.2.3.2.

Day 1 administration must be delayed in case of grade > 1 stomatitis or grade > 1 increase of transaminases (> 2.5 x ULN). Methotrexate must not be readministered before total recovery.

If recovery requires more than 2 weeks, methotrexate should be permanently discontinued.

Dose cancellation

Administration on day 8 must be cancelled in case of grade > 1 stomatitis or grade > 1 increase of transaminases (> 2.5 x ULN).

The protocol does not allow Day 8 dosing delay of methotrexate in case of non-haematological toxicity. Any delay of a methotrexate Day 8 dosing will be recorded as a delay and as a protocol deviation if it has been performed $\geq 7 + 4$ days since last Day 1 study drug administration (i.e., Day 11 or more).

Dose modifications

The table below outlines dose reduction for non-haematological toxicity.

Table 12: Dose modifications of methotrexate in Arm A for non-haematological toxicities

Non haematological toxicity after the previous administration	Dose adjustment for next administration
Stomatitis Grade 1 Grade 2 Grade \geq 3	Maintain the same dose Decrease one dose level Discontinue MTX
Transaminases > 2.5 x ULN and \leq 5.0 x ULN > 5.0 x ULN and \leq 20 x ULN	Decrease one dose level Discontinue MTX
Decreased creatinine clearance (Cockcroft-Gault) \leq 60 mL/min and \geq 20 mL/min < 20 mL/min	Decrease one dose level Discontinue treatment
Other grade \geq 3* toxicities	To be adjusted as medically indicated

* except grade 3 fatigue

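### Protocol 5.2.5 orders methotrexate 40 mg/m² when vinflunine stops in arm A, without excepting patients already cut to 20 mg/m², and the SAP has no planned intensity specific to those methotrexate-alone cycles

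*Protocol*

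**What the plan says.** Protocol 5.2.5 lets an arm A patient who stops one drug for toxicity stay on the other. If methotrexate stops, vinflunine continues at whatever level the patient has reached. If vinflunine stops, the rule is a fixed dose: "For patients who require discontinuation of vinflunine, methotrexate dosing must be increased to 40 mg/m² for at least one more cycle". No dosing days are given. After that, "if toxicity subsequently occurs, that requires treatment modifications of methotrexate, rules described in Arm B should apply".

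Protocol 5.2.1 sets the general rule: "After any dose reduction, this dose is then maintained with no re-escalation of doses in subsequent cycles". It also says that, for toxicity, "all dosing adjustment or delay should be applied to both drugs of arm A unless there is another specific recommendation".

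Arm A methotrexate starts at 30 mg/m² and has one reduced level, 20 mg/m² (Table 8). Table 11 (haematological toxicity) and Table 12 (stomatitis, transaminases, creatinine clearance) send patients there. Arm B has levels of 40, 30 and 20 mg/m² (Table 13).

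SAP Table 9-4 gives arm A one methotrexate planned dose, 60 mg/m² per three-week cycle or 20 mg/m²/week. SAP 9.2.4 takes planned intensity by arm from that table. SAP 9.2.9 asks for cycles, cumulative dose, dose intensity and RDI, by patient, for either drug given as monotherapy in arm A.

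**The concern.** For a patient at 20 mg/m² whose vinflunine then stops, the two protocol sections give different doses. Following 5.2.5 doubles a dose that was lowered for toxicity or for impaired clearance. Following 5.2.1 disregards a mandatory instruction in 5.2.5. An investigator cannot tell from the text which to do, and sites may differ.

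Renal function is the case that matters most. Entry requires this: "Adequate renal function: calculated (Cockcroft-Gault) creatinine clearance > 60 ml/min". Protocol 1.1.1 describes methotrexate as cleared mainly by the kidney.

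The SAP issue is one of reporting. The RDI for methotrexate-alone cycles would be measured against a regimen the patient is no longer meant to receive. Delivery would look better than it was, and some toxicity-driven reductions would read as full dose.

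**Working it through.** **Dose rules side by side, creatinine clearance 20 to 60 mL/min**

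| Rule | Methotrexate dose |
|---|---|
| Arm A, Table 12 with Table 8 | 30 → 20 mg/m² |
| Arm B, Table 17 with Table 13 | 40 → 30 mg/m² |
| Arm A once vinflunine stops, 5.2.5 | 40 mg/m² |

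A possible course: the patient enters with clearance above 60 mL/min; clearance falls into the 20 to 60 range and Table 12 cuts methotrexate to 20; grade 3 neuropathy then stops vinflunine (Table 7); 5.2.5 orders 40. That is 40/20 = 2 times the current dose and 40/30 = 1.33 times the arm B dose for the same clearance. The arm B rules enter only for toxicity that arises later, so read literally at least the first dose at 40 is ordered.

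The proviso in 5.2.1 about another specific recommendation is attached to the both-drugs sentence. It does not qualify the no-re-escalation sentence.

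There is a further route to 20 mg/m². Grade 2 neuropathy lowers vinflunine one level (Table 7), and Table 12 has no row for it. The both-drugs rule can therefore lower methotrexate as well, outside Tables 11 and 12.

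**Dosing days.** Section 5.2.5 is silent. Days 1 and 8 is the better-supported reading: Protocol 5.1.2 writes the arm B dose as a weekly dose and 5.2.5 does not; SAP 9.1.1 ends arm A treatment at the last methotrexate dose plus 14 days; SAP 9.2.6 foresees methotrexate cancellation in arm A on day 8 only. Weekly dosing is not excluded.

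**RDI.** The formulas are in SAP 9.2.1 to 9.2.4:

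- planned intensity = planned dose per cycle / 3 weeks
- RDI = actual intensity / planned intensity × 100

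Reproducing Table 9-4: arm A (2 × 30)/3 = 20; arm B (3 × 40)/3 = 40 mg/m²/week. Both match.

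Intensity ordered for methotrexate alone on days 1 and 8: (2 × 40)/3 = 26.7 mg/m²/week.

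| On-time cycle, days 1 and 8 | Intensity | RDI against 20 | RDI against 26.7 |
|---|---|---|---|
| 40 mg/m² | 80/3 = 26.7 | 133% | 100% |
| 30 mg/m² (cut for later toxicity) | 60/3 = 20 | 100% | 75% |
| 20 mg/m² (kept reduced) | 40/3 = 13.3 | 67% | 50% |

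Under the categories in SAP 9.2, the full cycle falls in the top class (110% or more). The 30 mg/m² cycle falls one class too high (90 to 110% instead of 70 to 90%). The 20 mg/m² cycle stays in the same class. The top class begins at 1.10 × 20 = 22 mg/m²/week, which is 22/26.7 = 82.5% of the ordered intensity.

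Per-patient illustration, with an assumed course of two full combination cycles then two full methotrexate-alone cycles: (60 + 60 + 80 + 80)/12 = 23.3; 23.3/20 = 117%.

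If dosing is weekly: 120/3 = 40; 40/20 = 200%.

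**The case against.** **The specific rule overrides the general one.** Section 5.2.1 is headed as general considerations and 5.2.5 covers one named situation. The latter keeps vinflunine at its current level but gives methotrexate a fixed 40, which is arm B's starting dose, so the contrast may be deliberate. This is a fair reading, but neither section states it. If it is right, the protocol knowingly doubles a dose lowered for toxicity, and that should be said openly.

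**Safeguards already exist.** After stomatitis or raised transaminases above grade 1, methotrexate waits for full recovery (5.2.3.3). Neutrophil and platelet thresholds apply on days 1 and 8 (5.2.3.2). Staying on methotrexate alone is optional, and the investigator may stop treatment. This stands, and it lowers the risk for those toxicities. It is weaker for clearance, for which Table 12 lowers the dose without requiring recovery. Chemistry before each cycle may prompt an investigator to apply a table, but 5.2.5 refers to the arm B tables only for later toxicity.

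**The right dose is a clinical choice.** Holding a patient at 20 on days 1 and 8 gives 13.3 mg/m²/week, one third of arm B's 40. That stands: the sponsor may prefer another level, but must state it.

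**133% is simply the defined result.** SAP 9.2.4 fixes planned intensity by arm, and 9.2.9 also reports absolute intensity, so a reader can rescale. It is correct that a planned intensity exists. A footnote naming the denominator would help, but a 30 mg/m² cycle would still sit in the 90 to 110% class.

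**Stronger readings a reader might infer.**

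- That every arm A patient moved to 40 breaches 5.2.1. Patients still at 30 have had no reduction, so they do not.
- That the SAP has no usable planned intensity at all. It has the combination value, and vinflunine alone keeps 93.33 mg/m²/week.
- That RDI will read 200%. That requires weekly dosing, which the documents do not state.

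**Conclusion.** The point holds and is minor. Sections 5.2.1 and 5.2.5 conflict for arm A patients already at 20 mg/m², and the text does not resolve it. The increase is twofold. With clearance of 20 to 60 mL/min the ordered dose exceeds what either arm's table allows. For stomatitis, transaminases and blood counts, existing rules give some protection.

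In the SAP, the gap is the lack of a planned intensity specific to methotrexate alone in arm A. The 133%, and the 100% in place of 75%, assume on-time cycles on days 1 and 8 and the default arm A denominator.

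Only RDI figures are affected. Dose reductions are tabulated separately (SAP 9.2.5.2) and single-agent cycles are listed (SAP 9.2.9). Overall survival does not use these quantities. How many patients had methotrexate cut and later stopped vinflunine cannot be derived from the documents.

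**What to change.** **Protocol 5.2.5.** Add:

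> The increase to 40 mg/m² does not apply to patients whose methotrexate was reduced for any reason, including under the both-drugs rule of 5.2.1; they continue at their current dose level.

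The exemption should not be limited to Tables 11 and 12, because the both-drugs rule can also bring a patient to 20. The sponsor should state the dosing days in the same paragraph.

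Cost: Protocol 15.1 requires an amendment. A dosing change is probably substantial, which means Ethics Committee and Competent Authority approval. Recruitment stopped on 16 October 2015, so it reaches only arm A patients still on treatment.

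**SAP Table 9-4.** Add a row for arm A methotrexate-alone cycles: 80 mg/m² per cycle, 3 weeks, 26.7 mg/m²/week (120 and 40 if the sponsor confirms weekly dosing). Use it for the monotherapy RDI in 9.2.9 and for the per-cycle categories of those cycles. Patients kept at 20 mg/m² then score 50% on days 1 and 8, so their reduction stays visible. Averaging planned intensities over a patient's cycles for the per-patient RDI in 9.2.4 is optional.

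Cost: one table row and no new data. This is worth doing even if no arm A patient remains on treatment.

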5.3. TREATMENT ASSIGNMENT

Patients will be randomised after written informed consent is obtained, all screening assessments (see

Table 18, Section 7.1) are performed and the health-related quality of life questionnaire is completed.

The investigator will determine a patient to be eligible and will enroll him/her by contacting the independent central registration center (either Interactive Voice Response System, IVRS, or Interactive Web Response System, IWRS).

Randomisation will be stratified according to a minimisation procedure (Pocock SJ, 1975) set up by the independent central registration centre, on the following factors:

- WHO performance status (0 versus 1)
- Refractory or resistant to platinum versus other
- Prior radiotherapy (yes versus no)
- Prior treatment with any anti-EGFR medication (yes versus no)
- Center

Randomisation and registration procedures are described in Section 7.2.

Patients withdrawn from the study retain their number. New patients must always be allotted a new patient number.

